### 11.5 Translational Endpoints

We assume that 90% of eligible patients will submit tissue and 80% of these will be successfully assayed. With 128 eligible patients enrolled on S1513, it is estimated that for each arm, 46 patients (n=92 total) will be included in analyses. The overall prevalence of each biomarker can be estimated to within 10% (95% confidence interval).

- a. The primary translational objective is to evaluate if *BRCA1* and *BRCA2* mutations (somatic or germline) are associated with improved clinical outcomes (OS, PFS, and ORR) in each treatment arm. Prevalences of *BRCA1* and *BRCA2* mutations in this patient population are estimated to be approximately 1-2% and 5-7%, respectively.
- b. Secondly, we will evaluate the impact of HRD positivity on clinical outcomes in each treatment arm. Although the HRD score threshold for positivity has yet to be determined in this disease, we will first dichotomize the score at its observed median value (represented as 50% prevalence in the tables below), and estimate the associations between that binary predictor and clinical outcomes. We will also assess the associations of HRD score as a continuous variable with clinical outcomes.
- c. Additionally, we will evaluate the impact of other exploratory genomic alterations (other than *BRCA1/2* mutations) identified by the BROCA-HR assay on clinical outcomes in each treatment arm.

We will evaluate if each potential biomarker is associated with the clinical outcomes of overall survival (OS), progression-free survival (PFS), and response rate (ORR) separately by treatment arm. The associations between each potential biomarker and both OS and PFS will be explored via Kaplan-Meier curves and Cox regression. We assume the baseline median OS is 6 months, 46 patients enrolled over 28 months and an additional 10 months of follow-up. The following table shows approximate power to detect OS hazard ratios of 2.5, 3, and 3.5, corresponding to median OS of 15, 18, and 21 months in the biomarker-positive subgroup, using a two-sided alpha of 0.1, for a range of biomarker frequencies.

| Biomarker Prevalence | Power  |        |          |
|----------------------|--------|--------|----------|
|                      | HR=2.5 | HR = 3 | HR = 3.5 |
| 5%                   | 30%    | 35%    | 39%      |
| 10%                  | 45%    | 54%    | 60%      |
| 25%                  | 73%    | 83%    | 89%      |
| 50%                  | 86%    | 93%    | 97%      |

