Assuming a baseline median PFS of 3 months, the following table shows approximate power to detect PFS hazard ratios of 2.5, 3, and 3.5, corresponding to median PFS of 7.5, 9, and 10.5 months in the biomarker-positive subgroup, using a two-sided alpha of 0.1, for a range of biomarker frequencies.

| Biomarker Prevalence | Power    |        |          |
|----------------------|----------|--------|----------|
|                      | HR = 2.5 | HR = 3 | HR = 3.5 |
| 5%                   | 35%      | 43%    | 50%      |
| 10%                  | 54%      | 65%    | 73%      |
| 25%                  | 82%      | 91%    | 95%      |
| 50%                  | 91%      | 97%    | 99%      |

Assuming a null ORR of 10%, the following table describes the approximate power to detect differences in response rate of 25%, 30%, and 35% (corresponding to ORR of 35%, 40%, and 45%) in the biomarker-positive sub-group, using a two-sided 0.1 level test of proportions across a range of biomarker frequencies.

| Biomarker Prevalence | Power           |                 |                 |
|----------------------|-----------------|-----------------|-----------------|
|                      | $\Delta = 25\%$ | $\Delta = 30\%$ | $\Delta = 35\%$ |
| 10%                  | 20%             | 30%             | 39%             |
| 25%                  | 44%             | 56%             | 67%             |
| 50%                  | 50%             | 64%             | 76%             |

We also plan to estimate an HRD score threshold for positivity in this population by applying receiver operating characteristic curves, classifying patients by overall disease response. The precision of this estimate will depend not only on the number of patients with available data but also on the prevalence of disease response.

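### With about 3 to 5 BRCA1/2-positive patients per arm, no standard Cox statistic holds the stated two-sided alpha of 0.1, and the power in the 5% and 10% rows depends on a test the plan does not name

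*Combined protocol and SAP*

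**What the plan says.** Section 11.5 makes the association of BRCA1/2 mutations with better OS, PFS and ORR in each arm the primary translational objective. On numbers, "it is estimated that for each arm, 46 patients (n=92 total) will be included in analyses". Associations of each marker with OS and PFS "will be explored via Kaplan-Meier curves and Cox regression", each arm being analysed on its own.

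For OS the design inputs are: "We assume the baseline median OS is 6 months, 46 patients enrolled over 28 months and an additional 10 months of follow-up". The OS table gives "approximate power to detect OS hazard ratios of 2.5, 3, and 3.5", "using a two-sided alpha of 0.1, for a range of biomarker frequencies". The PFS table uses the same hazard ratios and alpha, and begins: "Assuming a baseline median PFS of 3 months". Both tables have rows at 5%, 10%, 25% and 50% prevalence.

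BRCA1 and BRCA2 prevalences "in this patient population are estimated to be approximately 1-2% and 5-7%, respectively". Appendix 18.4 gives 7-10% for the two genes together and treats BRCA1/2 testing as an integrated biomarker.

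The section does not say which Cox statistic supplies the p-value. It names no exact or permutation method and sets no minimum number of positives or events.

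**The concern.** The 5% and 10% rows are the ones that bracket BRCA1/2, and in them the marker-positive group contributes about one to four events. A normal approximation cannot be relied on there, for the error rate or for the power. The score, Wald and likelihood-ratio versions of the Cox test, which agree in large samples, also separate. A reader who takes the table at face value expects 5% error in each tail and a known chance of detecting a large benefit. If neither holds, the main biomarker question is tested at an unknown and uneven error level. With the statistic left open, conflicting p-values could also be chosen between after the data are seen.

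**Working it through.** **Inputs.** From Section 11.5: 46 patients per arm (128 × 0.9 × 0.8 / 2 = 46.1); median OS 6 months and PFS 3 months in marker-negatives; HR 2.5/3/3.5, meaning medians multiplied by that factor in marker-positives; 28 months accrual plus 10 months follow-up; two-sided alpha 0.1 (z = 1.645). BRCA1/2 prevalence is (1-2%) + (5-7%) = 6-9% if carriers do not overlap, or 7-10% in Appendix 18.4. 46 × 0.06 = 2.8 and 46 × 0.10 = 4.6, so about 3 to 5 positives per arm. Assumed: exponential survival, uniform accrual, administrative censoring only.

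**Step 1: reproduce the table.** The chance of an observed event is 1 − [exp(−10λ) − exp(−38λ)]/(28λ), with λ = ln 2/median. For OS this is 0.906 at a median of 6 months and 0.647 at 15 months. At 5% prevalence and HR 2.5:

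- E_pos = 46 × 0.05 × 0.647 = 1.49
- E_neg = 46 × 0.95 × 0.906 = 39.6
- √(1/1.49 + 1/39.6) = 0.835
- ln 2.5/0.835 = 1.097
- power = Φ(1.097 − 1.645) = 29.2%, against 30% stated

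The same formula gives 29.2/34.7/38.9% across the OS 5% row and 35.0/43.0/49.3% across the PFS 5% row. It matches all 24 OS and PFS cells within 1 point. The arithmetic is therefore sound as a large-sample approximation. Expected events in positives behind the low rows are 1.2-1.5 (5%) and 2.4-3.0 (10%) for OS, and 1.8-2.0 and 3.5-3.9 for PFS.

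**Step 2: actual size.** Arms were simulated under the same assumptions with no marker effect, the number of positives Binomial(46, prevalence), and no rejection if there are none. Cells show total rejection (benefit tail / harm tail), in %, at nominal 10 (5 / 5).

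| | Log-rank (score) | Wald | Likelihood-ratio |
|---|---|---|---|
| OS, 5% | 14.7 (2.4 / 12.3) | 11.7 (1.1 / 10.6) | 12.3 (4.8 / 7.5) |
| OS, 10% | 13.5 (3.1 / 10.3) | 11.8 (2.4 / 9.4) | 11.8 (4.7 / 7.1) |
| PFS, 5% | 14.8 (2.7 / 12.1) | 11.7 (1.3 / 10.4) | 11.8 (4.5 / 7.3) |
| PFS, 10% | 13.6 (3.2 / 10.4) | 12.2 (2.7 / 9.6) | 11.8 (4.6 / 7.2) |

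Holding the OS positives fixed at 2/3/4/5, log-rank size is 15.9/14.1/13.6/12.1%, Wald 12.9/12.2/12.2/11.1% and likelihood-ratio 12.6/12.1/11.9/11.1%. With 12 or 23 positives (the 25% and 50% rows) size is 10.4-11.3% and power is close to the table.

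**Step 3: power towards benefit**, HR 2.5/3/3.5, in %.

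| | Stated | Wald | Log-rank | Likelihood-ratio |
|---|---|---|---|---|
| OS, 5% | 30/35/39 | 13/16/18 | 24/31/35 | 34/42/48 |
| OS, 10% | 45/54/60 | 35/42/48 | 42/51/60 | 49/58/67 |
| PFS, 5% | 35/43/50 | 19/24/28 | 29/37/44 | 37/45/51 |
| PFS, 10% | 54/65/73 | 43/53/61 | 48/58/67 | 53/64/72 |

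Wald is 10-22 points low and log-rank 0-7 points low. The likelihood-ratio test is above the OS table and within about 2 points of the PFS table. Repeat simulations agreed to within about 2 points.

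One source of the Wald loss is an arm in which no positive patient has an event: the estimated log hazard ratio then runs to minus infinity, its standard error grows faster, and the Wald statistic tends to zero.

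**Step 4: the alternative.** An equal-tail permutation log-rank test at 0.10 rejects towards benefit 4.8-5.7% of the time under no effect. Its OS power for HR 2.5/3/3.5 is 32/40/45% with 2 positives, 41/50/59% with 3 and 53/64/72% with 5. For PFS it is 37/44/52%, 46/56/64% and 60/71/80%. The tails must be handled separately: a permutation test on the absolute score rejects 9.7% towards benefit under no effect with 2 positives.

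**The case against.** Several points on the other side are fair.

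- **The power shortfall is not a property of the plan as written.** The section names Cox regression, not the Wald test, and the log-rank test in Sections 11.2 and 11.4 is for treatment comparisons. A reader might infer that the study has much less power for BRCA1/2 than tabulated. That follows only if Wald is used; the likelihood-ratio test is at or above the OS figures. What stands is that the statistic is open and the choice matters.
- **The 5% row is below the BRCA range.** At 7.5% the plan's formula gives 38/45/51% for OS; simulation gives about 34/42/49% (log-rank), 42/51/58% (likelihood-ratio) and 24/29/34% (Wald). Apart from Wald these are modest departures. It is tempting to say a Cox analysis would almost never detect benefit, but that fits only Wald with exactly two positives (about 4% for OS).
- **The excess error is on the harm side.** One might infer that the plan would over-declare benefit. It would not: the benefit tail is at or below 5% for all three statistics.
- **The analyses are exploratory, the power is labelled approximate, and the Revision #1 memo says accrual is permanently closed.** Recomputed rows cannot change the design. Still, those labels do not cover a tail split of 2.4% against 12.3% where 5% and 5% is implied, and the choice of p-value still governs how the BRCA1/2 result is read.

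**Conclusion.** The point holds in a limited form. At the prevalence the protocol gives for BRCA1/2, no standard Cox statistic has a two-sided alpha of 0.1. For OS at 5-10% prevalence the actual size is about 13-15% (log-rank) and about 12% (Wald and likelihood-ratio), with score and Wald errors mostly in the harm tail. Power in those rows may be roughly half the stated figure or somewhat above it, depending on a statistic the plan does not name. The table's arithmetic is not in error, its 25% and 50% rows are close to right, and the primary OS analysis is untouched. Severity is minor to moderate.

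This rests on exponential survival, the stated accrual and follow-up, 46 assayed patients per arm, and marker status independent of censoring. The combined 6-9% figure assumes that BRCA1 and BRCA2 carriers do not overlap.

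**What to change.** In Section 11.5, state that for markers with few positives in an arm, BRCA1/2 in particular, the OS and PFS p-values will come from an equal-tail permutation log-rank test (twice the smaller one-sided p-value), with profile-likelihood intervals for the Cox hazard ratio. Fix in advance the number of positives below which this applies. The likelihood-ratio test alone is not enough, since its two-sided size is still about 12%.

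Restate the 5% and 10% rows of the OS and PFS tables by simulation for that test, letting the number of positives vary. The chance of at most one positive in an arm is 32% at 5% prevalence, 16% at 7% and 5% at 10%, so the restated rows should say how such arms are counted.

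The cost is a sentence or two, two rows in each of two tables and a little computing. The stated power changes slightly; no patients, specimens or visits are added.

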#### 11.6 Data and Safety Monitoring

A Data and Safety Monitoring Committee will oversee the conduct of the study. The Committee consists of four members from outside of the SWOG, 3 SWOG members, 3 non-voting representatives from the National Cancer Institute (NCI), and the Group Statistician (non-voting). The members of this Committee will receive confidential reports every 6 months from the SWOG Statistical Center, and will meet at the Group's bi-annual meetings as necessary. The Committee will be responsible for decisions regarding possible termination and/or early reporting of the study.

#### 12.0 DISCIPLINE REVIEW

Discipline review is not applicable in this study.

#### 13.0 REGISTRATION GUIDELINES

##### 13.1 Registration Timing

Patients must be registered prior to initiation of treatment (no more than five working days prior to planned start of treatment).

##### 13.2 Investigator/Site Registration

Prior to the recruitment of a patient for this study, investigators must be registered members of a NCTN Group. Each investigator must have an NCI investigator number and must maintain an "active" investigator registration status through the annual submission of a complete investigator registration packet to CTEP.

##### a. CTEP Investigator Registration Procedures

Food and Drug Administration (FDA) regulations and National Cancer Institute (NCI) policy require all investigators participating in any NCI-sponsored clinical trial to register and to renew their registration annually.

Registration requires the submission of:

- a completed **Statement of Investigator Form** (FDA Form 1572) with an original signature
- a current Curriculum Vitae (CV)
- a completed and signed **Supplemental Investigator Data Form** (IDF)
- a completed **Financial Disclosure Form** (FDF) with an original signature

Fillable PDF forms and additional information can be found on the CTEP website at <[http://ctep.cancer.gov/investigatorResources/investigator\\_registration.htm](http://ctep.cancer.gov/investigatorResources/investigator_registration.htm)>.

For questions, please contact the **CTEP Investigator Registration Help Desk** by email at <[[contact]](mailto:[contact])>.

b. CTEP Associate Registration Procedures

The Cancer Therapy Evaluation Program (CTEP) Identity and Access Management (IAM) application is a web-based application intended for use by both Investigators (i.e., all physicians involved in the conduct of NCI-sponsored clinical trials) and Associates (i.e., all staff involved in the conduct of NCI-sponsored clinical trials).

Associates will use the CTEP-IAM application to register (both initial registration and annual re-registration) with CTEP and to obtain a user account.

Investigators will use the CTEP-IAM application to obtain a user account only. (See CTEP Investigator Registration Procedures above for information on registering with CTEP as an Investigator, which must be completed before a CTEP-IAM account can be requested.)

An active CTEP-IAM user account will be needed to access all CTEP and CTSU (Cancer Trials Support Unit) websites and applications, including the CTSU members' website.

Additional information can be found on the CTEP website at <[http://ctep.cancer.gov/branches/pmb/associate\\_registration.htm](http://ctep.cancer.gov/branches/pmb/associate_registration.htm)>. For questions, please contact the **CTEP Associate Registration Help Desk** by email at <[[contact]](mailto:[contact])>.

c. CTSU Registration Procedures

Each investigator or group of investigators at a clinical site must obtain IRB approval for this protocol and submit IRB approval and supporting documentation to the CTSU Regulatory Office before they can be approved to enroll patients. Study centers can check the status of their registration packets by querying the Regulatory Support System (RSS) site registration status page of the CTSU members' website by entering credentials at <https://www.ctsu.org>. For sites under the CIRB initiative, IRB data will automatically load to RSS.

Note: Sites participating on the NCI CIRB initiative and accepting CIRB approval for the study are not required to submit separate IRB approval documentation to the CTSU Regulatory Office for initial, continuing or amendment review. This information will be provided to the CTSU Regulatory Office from the CIRB at the time the site's Signatory Institution accepts the CIRB approval. The Signatory site may be contacted by the CTSU Regulatory Office or asked to complete information verifying the participating institutions on the study. Other site registration requirements (i.e., laboratory certifications, protocol-specific training certifications, or modality credentialing) must be submitted to the CTSU Regulatory Office or compliance communicated per protocol instructions.

1. Downloading Site Registration Documents:

Site registration forms may be downloaded from the **S1513** protocol page located on the CTSU members' website.

- Go to <https://www.ctsu.org> and log in to the members' area using your CTEP-IAM username and password
- Click on the Protocols tab in the upper left of your screen
- Click on the By Lead Organization folder to expand
- Click on the SWOG link to expand, then select trial protocol **S1513**
- Click on LPO Documents, select the Site Registration documents link, and download and complete the forms provided.

2. Requirements for **S1513** Site Registration:

- CTSU IRB Certification (for sites not participating via the NCI CIRB)
- CTSU IRB/Regulatory Approval Transmittal Sheet (for sites not participating via the NCI CIRB)

3. Submitting Regulatory Documents:

Submit completed forms along with a copy of your IRB Approval to the CTSU Regulatory Office, where they will be entered and tracked in the CTSU RSS.

CTSU Regulatory Office  
[name]  
[name]  
[contact]  
[contact]

E-mail: [[contact]](mailto:[contact]) (for regulatory document submission only)

4. Checking Your Site's Registration Status:

Check the status of your site's registration packets by querying the RSS site registration status page of the members' section of the CTSU website. (Note: Sites will not receive formal notification of regulatory approval from the CTSU Regulatory Office.)

- Go to <https://www.ctsu.org> and log in to the members' area using your CTEP-IAM username and password
- Click on the Regulatory tab at the top of your screen
- Click on the Site Registration tab

Enter your 5-character CTEP Institution Code and click on Go

### 13.3 OPEN Registration Requirements

The individual registering the patient must have completed the appropriate SWOG Registration Worksheet. The completed form must be referred to during the registration but should not be submitted as part of the patient data.

Patient enrollment will be facilitated using the Oncology Patient Enrollment Network (OPEN). OPEN is a web-based registration system available on a 24/7 basis. To access OPEN, the site user must have an active CTEP-IAM account (check at < <https://eapps-ctep.nci.nih.gov/iam/index.jsp> >) and a 'Registrar' role on either the LPO or participating organization roster.

OPEN will also ask additional questions that are not present on the SWOG Registration Worksheet. The individual registering the patient must be prepared to provide answers to the following questions:

- a. Institution CTEP ID

- b. Protocol Number
- c. Registration Step
- d. Treating Investigator
- e. Credit Investigator
- f. Patient Initials
- g. Patient's Date of Birth
- h. Patient SSN (SSN is desired, but optional. Do not enter invalid numbers.)
- i. Country of Residence
- j. ZIP Code
- k. Gender (select one):
  - Female Gender
  - Male Gender
- l. Ethnicity (select one):
  - Hispanic or Latino
  - Not Hispanic or Latino
  - Unknown
- m. Method of Payment (select one):
  - Private Insurance
  - Medicare
  - Medicare and Private Insurance
  - Medicaid
  - Medicaid and Medicare
  - Military or Veterans Sponsored NOS
  - Military Sponsored (Including Champus & Tricare)
  - Veterans Sponsored
  - Self Pay (No Insurance)
  - No Means of Payment (No Insurance)
  - Other
  - Unknown
- n. Race (select all that apply):
  - American Indian or Alaska Native
  - Asian
  - Black or African American
  - Native Hawaiian or other Pacific Islander
  - White
  - Unknown

#### 13.4 Registration Procedures

- a. All site staff will use OPEN to enroll patients to this study. OPEN is integrated with the CTSU Enterprise System for regulatory and roster data and, upon enrollment, initializes the patient in the Rave database. OPEN can be accessed at <https://open.ctsu.org>, from the OPEN tab on the CTSU members' side of the website at <https://www.ctsu.org>, or from the OPEN Patient Registration link on the SWOG CRA Workbench.

- b. Prior to accessing OPEN site staff should verify the following:
    - All eligibility criteria have been met within the protocol stated timeframes and the affirmation of eligibility on the Registration Worksheet has been signed by the registering investigator or another investigator designate. Site staff should refer to [Section 5.0](#) to verify eligibility.
    - All patients have signed an appropriate consent form and HIPAA authorization form (if applicable).
  - c. The OPEN system will provide the site with a printable confirmation of registration and treatment information. Please print this confirmation for your records.
  - d. Further instructional information is provided on the OPEN tab on the CTSU members' side of the website at <https://www.ctsu.org> or at <https://open.ctsu.org>. For any additional questions contact the CTSU Help Desk at [name] or [[contact]](mailto:[contact]).
- 13.5 Exceptions to SWOG registration policies will not be permitted.
- a. Patients must meet all eligibility requirements.
  - b. Institutions must be identified as approved for registration.
  - c. Registrations may not be cancelled.
  - d. Late registrations (after initiation of treatment) will not be accepted.

## 14.0 DATA SUBMISSION SCHEDULE

### 14.1 Data Submission Requirement

Data must be submitted according to the protocol requirements for **ALL** patients registered, whether or not assigned treatment is administered, including patients deemed to be ineligible. Patients for whom documentation is inadequate to determine eligibility will generally be deemed ineligible

### 14.2 Master Forms

Master forms can be found on the protocol abstract page on the SWOG website ([www.swog.org](http://www.swog.org)) and (with the exception of the sample consent form and the Registration Worksheet) must be submitted on-line via the Web; see [Section 14.3a](#) for details.

### 14.3 Data Submission Procedures

- a. Data collection for this study will be done exclusively through the Medidata Rave® clinical data management system. Access to the trial in Rave is granted through the iMedidata application to all persons with the appropriate roles assigned in Regulatory Support System (RSS). To access Rave via iMedidata, you must have an active CTEP-IAM account (check at <https://eapps-ctep.nci.nih.gov/iam/index.jsp>) and the appropriate Rave role (Rave CRA, Read-Only, Site Investigator) on either the LPO or participating organization roster at the enrolling site.

Upon initial site registration approval for the study in RSS, all persons with Rave roles assigned on the appropriate roster will be sent a study invitation e-mail from

iMedidata. To accept the invitation, site users must log into the Select Login (<https://login.imedidata.com/selectlogin>) using their CTEP-IAM user name and password, and click on the "accept" link in the upper right-corner of the iMedidata page. Please note, site users will not be able to access the study in Rave until all required Medidata and study specific trainings are completed. Trainings will be in the form of electronic learnings (eLearnings), and can be accessed by clicking on the link in the upper right pane of the iMedidata screen.

Users that have not previously activated their iMedidata/Rave account at the time of initial registration approval for the study in RSS will also receive a separate invitation from iMedidata to activate their account. Account activation instructions are located on the CTSU website, Rave tab under the Rave resource materials (Medidata Account Activation and Study Invitation Acceptance). Additional information on iMedidata/Rave is available on the CTSU members' website under the Rave tab at [www.ctsu.org/RAVE/](http://www.ctsu.org/RAVE/) or by contacting the CTSU help Desk at [name] or by e-mail at [[contact]](mailto:[contact])

- b. You may also access Rave® via the SWOG CRA Workbench. Go to the SWOG web site (<http://swog.org>) and logon to the Members Area using your SWOG Roster ID Number and password. After you have logged on, click on *Workbenches*, then *CRA Workbench* to access the home page for the CRA Workbench and follow the link to Rave® provided in the left-hand navigation panel.

To access the CRA Workbench the following must be done (in order):

1. You are entered into the SWOG Roster and issued a SWOG Roster ID Number,
2. You are associated as an investigator or CRA/RN at the institution where the patient is being treated or followed,
3. Your Web User Administrator has added you as a web user and has given you the appropriate system permissions to view data for that institution.

For assistance with points 1 and 2 call the Operations Office at [name]. For point 3, contact your local Web User Administrator (refer to the "Who is my Web User Administrator?" function on the [swog.org](http://swog.org) Members logon page).

For difficulties with the CRA Workbench, please email [[contact]](mailto:[contact]).

- c. Institutions participating through the Cancer Trials Support Unit (CTSU), please refer to the CTSU Participation Table.

